4. STUDY DESIGN

The primary objective is to define the natural history of BK viremia in renal or renal-pancreas transplant recipients. In order to understand the natural history of infection, we will measure the time to the development of BK viremia and its correlation with progression to end-organ disease (BKVN or BK hemorrhagic cystitis). Data from this intensive natural history monitoring period will allow for the identification of the types of high-risk patients who might benefit from future studies of therapeutic interventions for BKV infection, when effective therapy becomes available. This will be accomplished by serial quantitative BK DNA measurements by PCR in blood (plasma). It is anticipated that most samples (blood and urine) will be collected during routine standard-of-care clinic visits and will not require extra study visits. Phases of the study can be summarized as follows:

- Subject identification and informed consent. Informed consent should be obtained in the peri-transplant period (between 7 days pre-transplantation [T-7d] and 100 days post-transplantation [T+100 d]).
- Prospective screening for BK viremia. Enrollment and initiation of specimen collection should begin no sooner than 4 weeks after transplantation. Enrollment cannot occur later than 100 days after transplantation. **Subjects will be screened (collection of blood and urine for laboratory studies, including BK PCR) approximately monthly for 6 months (timed from the date of transplantation), then every other month for 6 months. For subjects who remain BKV-negative, screening will terminate approximately 12 months from the date of transplantation.**
- Intensive sampling of subjects identified with BK viremia. Subjects identified with qualifying viremia will be sampled approximately every two weeks until resolution of viremia (defined as PCR negative, or <1000 copies).
Note: Patients who did not participate in the prospective screening phase but are identified with BK viremia by standard-of-care testing may be enrolled, as long as they are still within 90 days of transplantation.
- Post-viremia follow-up. Following resolution of viremia, subjects will be sampled (collection of blood and urine) approximately monthly for 6 months (unless another termination event occurs sooner).

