4.3. Intensive Sampling Phase

Approximately 40 viremic subjects (up to a maximum of 60) will be asked to participate in more intensive sampling. Those subjects in whom BK viremia is identified (by PCR result demonstrating BK DNA $\geq 10,000$ copies/ml) will be shifted to a more intensive sampling schedule. A review of the informed consent will be initiated by the research staff to confirm the subject's continued willingness and ability to participate in the intensive monitoring phase until resolution of viremia or until another discontinuation event occurs.

Blood and urine specimen collection will occur every 2 weeks, \pm 7 days, until the BK viremia has resolved (or another study termination endpoint is reached). Resolution of BK viremia is defined as PCR becoming negative (or viral load <1000 copies/ml). Start and stop dates for the Intensive Sampling Phase will be defined by the date that the qualifying (initial positive and subsequent negative) blood samples were drawn.

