5. Obtain 10 ml of blood for study-specified PCR assays (BK and other viruses), to be performed at the UAB Central Laboratory. Blood will be collected, separated to plasma, then stored and shipped per instructions in the Manual of Procedures; If blood BK PCR was performed for routine standard-of-care at a local or reference laboratory, record the results of that assay in the research record;
6. Optional urinalysis - if UA was performed for routine standard-of-care within 7 days of enrollment, then the results of those assays can be recorded);
7. Obtain urine (approximately 100 ml) for subsequent study-specified PCR assays (BK and other viruses) and measurements of urinary biomarkers to be performed at the UAB Central Laboratory. Urine will be collected, stored, and shipped per instructions in the Manual of Procedures.
8. Notify the UAB Central Unit if the subject has consented to any other research study.

6.3. Intensive Monitoring Phase for BK Viremic Subjects: (approximately every 2 weeks +/- 7 days until viremia has resolved (PCR negative or <1000 copies/ml), then approximately every 4 weeks +/-14 days for 6 months).

At each protocol-defined study visit, the following events will occur:

1. Document interval medical history to specifically include:
 - a. subject death,
 - b. loss of graft function as defined by GFR <10 mL/min/1.73 m²
 - c. development of urinary outlet obstruction
 - d. development of gross hematuria
 - e. development of lymphocele
 - f. acute rejection
 - g. initiation of dialysis
 - h. re-transplantation
 - i. renal biopsies – Should renal biopsy be performed per standard-of-care during the course of the study, record the results from the pathology report.
2. Document use of selected concomitant medications (specifically, antiviral agents, immunomodulators, and immunosuppressive medications – see MOP for listing);
3. Record blood concentrations of immunosuppressive drugs obtained for clinical care purposes;
4. Obtain blood for determination of creatinine and GFR. If results of serum creatinine and GFR obtained for clinical care purposes (within 7 days) are available, those results may be used instead;

5. Obtain 10 ml of blood for study-specified PCR assays (BK and other viruses), to be performed at the UAB Central Laboratory. Blood will be collected, separated to plasma, then stored and shipped per instructions in the Manual of Procedures;

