6.4. Subject Early Termination

Subjects will be terminated from the study for any of the following reasons:

- Death;
- Initiation of chronic dialysis for loss of graft function;
- Re-transplantation;
- Inability or unwillingness to comply with study requirements.

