6.5. Management of Subject Withdrawals

Study subjects may withdraw voluntarily from participation in the study at any time. If a study subject withdraws or is discontinued from the study at any time prior to completion of the study, the reason for this decision will be recorded on the study termination page of the eCRF.

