We are also interested in comparing the change in GFR between those with and without BKV viremia. In this power analysis, we will only be concerned about the change from baseline (time of enrollment) to Month 12 (time post-transplant). Assuming the standard deviation of the change in GFR is assumed to be the same for those with and without BKV viremia and equals 10.9 ml/min/1.73 m² (Ref: Srinivas TR, Flechner SM, Poggio ED, et al. Glomerular filtration rate slopes have significantly improved among renal transplants in the United States. Transplantation 2010; 90:1499-505.). With 40 BKV viremia subjects and 410 non-BKV viremia subjects, we will detect a mean difference in the change in GFR of at least 5.9 ml/min/1.73 m² with 90% power between these two groups of subjects at 5% level of significance based on a t-test. In the final analysis, we will be using all available GFR data for each subject which should increase the power as more information is used. This will enable us to still use data from subjects who dropped out before the end of the study.

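### Section 6.4 ends all data collection on subjects with a working graft who cannot or will not comply, so GFR and outcome data that routine care may still produce are not collected, possibly at a higher rate in viremic subjects

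*Combined protocol and SAP*

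**What the plan says.** Section 6.4 lists four reasons for termination from the study: death, chronic dialysis for graft loss, re-transplantation, and "Inability or unwillingness to comply with study requirements". Only the fourth removes a living subject whose graft is working. For anyone who withdraws or is discontinued, Section 6.5 says that "the reason for this decision will be recorded on the study termination page of the eCRF". It asks for nothing else.

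GFR and the listed clinical events are recorded at protocol visits (Sections 6.1 to 6.3). Much of this already comes from routine care. Section 6.3, item 4, states: "If results of serum creatinine and GFR obtained for clinical care purposes (within 7 days) are available, those results may be used instead". Section 4.6 takes biopsy results from the pathology report, and Section 7.1 takes history from medical charts.

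The schedule depends on viremia. Screening runs "approximately monthly for 6 months (timed from the date of transplantation), then every other month for 6 months" (Section 4). After qualifying viremia, "Blood and urine specimen collection will occur every 2 weeks" until resolution (Section 4.3), and then about monthly for 6 months. At that switch, staff review the consent "to confirm the subject's continued willingness and ability to participate in the intensive monitoring phase".

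Section 8.2.1 bases the GFR power on a t-test "With 40 BKV viremia subjects and 410 non-BKV viremia subjects", with SD 10.9 and a detectable difference of 5.9 ml/min/1.73 m² at 90% power. It adds that the final analysis will use all available GFR values, including those of dropouts. Section 8.4.1 specifies a mixed model for repeated measures, and Section 8.4 rules out imputation.

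**The concern.** The study has no intervention, so a subject who stops study visits has not left any treatment under test. Such a subject may well stay in transplant care and go on producing the creatinine values and events the study needs. The rule as written stops their collection.

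Two results are exposed. The first is the GFR comparison between viremic and non-viremic subjects, which is a primary objective (Section 3.1.1). The mixed model keeps values obtained before exit, but it relies on later GFR being predictable from them. Exit through inability to comply may accompany illness, which is where that assumption is weakest. The second is the set of outcome frequencies in Section 3.2.2. Death, dialysis, re-transplantation, rejection or biopsy after exit go unrecorded, and no model of GFR recovers them.

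The loss may also be related to exposure. Viremia shortens the scheduled interval and adds a point at which a subject is asked again about taking part, and the viremic group is the small one.

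**Working it through.** **1. What happens after termination.** Sections 4.2, 4.4, 6.4 and 6.5 were read together for any step after a subject stops for non-compliance. They require the reason for termination. None describes chart abstraction or a check of graft or vital status.

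**2. Scheduled sampling.** Visits per 26 weeks:
- every 8 weeks: 26/8 = 3.25
- every 4 weeks: 26/4 = 6.5
- every 2 weeks: 26/2 = 13

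Scheduled frequency therefore doubles from the 4-week schedule and quadruples from the 8-week schedule while viremia lasts. This counts scheduled sampling, not extra trips to the clinic.

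**3. The plan's own power figure.** Inputs from Section 8.2.1: n = 40 and 410, SD 10.9, difference 5.9, 5% level (taken as two-sided).
- SE = 10.9 × √(1/40 + 1/410) = 1.806
- Noncentrality = 5.9/1.806 = 3.27, with 448 degrees of freedom
- Power from the noncentral t = 0.903, and the difference detectable at 90% power is 5.87

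The stated 5.9 at 90% reproduces. It counts all 450 subjects, with no allowance for loss.

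**4. Power if Month 12 GFR is lost.** The documents give no dropout rate, so the rates below are assumptions. Loss in the non-viremic group is set at 5% (410 × 0.95 ≈ 390). The formula is the same as in step 3.

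| Viremic loss | n viremic / non-viremic | Power at 5.9 | Detectable difference, 90% power |
|---|---|---|---|
| none (plan) | 40 / 410 | 0.903 | 5.87 |
| 10% | 36 / 390 | 0.873 | 6.17 |
| 15% | 34 / 390 | 0.855 | 6.33 |
| 25% | 30 / 390 | 0.813 | 6.71 |

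These are worst cases for precision, because a lost subject contributes nothing.

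**5. Which group's loss matters.** With one group complete, 20% loss in the viremic group (32 vs 410) gives power 0.837. The same 20% in the non-viremic group (40 vs 328) gives 0.897. Precision depends almost entirely on the viremic group.

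**6. Counts lost.** In step 4, about 20 non-viremic subjects are lost, against 4, 6 or 10 viremic subjects. Viremic losses would be the larger number only if their rate were more than 410/40 = 10.25 times the non-viremic rate.

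**7. Bias.** Write p for the share lost and g for how much worse the change in GFR is in those lost than in those retained. Before any credit for the mixed model, the group difference is understated by p(viremic) × g(viremic) − p(non-viremic) × g(non-viremic). With the loss rates of step 4 and an assumed common g of 5 to 10, this runs from (0.10 − 0.05) × 5 = 0.25 to (0.25 − 0.05) × 10 = 2.0 ml/min/1.73 m². With equal rates and equal gaps it is zero. Neither p nor g is in the documents.

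**The case against.** The strongest reply is that the rule will rarely be used. Section 4.9 calls all post-enrollment visits and windows approximate and dependent on the subject's availability. Section 4 expects most samples to be taken at routine clinic visits. A reader might infer from the termination rule that a missed two-weekly visit ends participation. The text does not say so, and the fourth bullet more naturally covers subjects who stop taking part. This stands, and it lowers the expected frequency. It does not change what happens once a subject is terminated, and it makes later chart data more likely to exist.

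A reader might also infer that the losses would fall mainly in the viremic group. Step 6 shows that this does not follow. A higher rate is plausible, but larger numbers would need a rate more than ten times higher, and no figure in the documents supports even a higher rate.

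The power illustration is fixed at 40 viremic subjects, whereas Section 8.2.1 allows up to 60. At 11% viremia, 450 × 0.11 = 49.5 are expected. The same loss rates then leave 44.6, 42.1 or 37.1 viremic subjects against 380.5, with power 0.93, 0.91 or 0.88. Headroom of that kind would absorb much of the loss of precision. It would not recover missing events or remove bias.

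The primary endpoint listed in Section 3.2.1 is the incidence of viremia. A subject who leaves after qualifying viremia has already been counted there, so exit after viremia does not affect it.

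Finally, Section 6.5 does not forbid further recording, and the Manual of Procedures and the consent form were not available for this review. Either could provide for chart access. If so, Sections 6.4 and 6.5 should cite that provision.

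**Conclusion.** The point holds as a gap in data collection. Followed as written, Sections 6.4 and 6.5 give up GFR and outcome data that routine care may produce and that the protocol already accepts from the record. It is worth correcting because one primary objective rests on about 40 viremic subjects and the correction is cheap.

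The size is uncertain. Under the assumed loss rates, power at 5.9 falls from 0.90 to at worst 0.87, 0.86 or 0.81, and by less if the mixed model draws on values before exit or more than 40 viremic subjects are found. The size and direction of any bias depend on how lost subjects differ from retained ones in both groups, which the documents do not state. The range in step 7 shows how it would arise and is not an estimate. That loss will be higher among viremic subjects is a reasonable inference from the schedule and the renewed willingness check, but it is not shown. The documents do not support concluding that the GFR comparison is underpowered or biased as it stands.

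**What to change.** Reword the fourth bullet of Section 6.4 so that a subject who is unable or unwilling to comply stops study visits and sampling only. Unless the subject withdraws consent for data use, the site then records from the chart:
- the clinical-care creatinine and GFR nearest to Month 12 post-transplant, within a window the protocol states (the present 7-day allowance is tied to a study visit and would not serve here);
- dialysis, re-transplantation, biopsy, acute rejection and vital status, up to the planned end of that subject's phase.

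Apply the same rule to viremic subjects who decline the intensive phase in Section 4.3. State that these values enter the GFR model in Section 8.4.1 and the outcome counts in Section 3.2.2. Report dropout by viremia status, with reasons.

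The cost is a protocol wording change, possibly one sentence in the consent form, and one or two chart reviews per affected subject. No visit or procedure is added. Where care moves away from the site, the chart may be incomplete, and the report should say for how many subjects this was so.

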6.5. Management of Subject Withdrawals

Study subjects may withdraw voluntarily from participation in the study at any time. If a study subject withdraws or is discontinued from the study at any time prior to completion of the study, the reason for this decision will be recorded on the study termination page of the eCRF.

6.6. Termination of Study

The UAB Central Unit (in consultation with DMID) and NIH/NIAID have the right to terminate this study at any time. Reasons for terminating the study may include, but are not limited to, the following:

- Study subject enrollment is unsatisfactory;
- Data recording is inaccurate or incomplete;
- Investigators do not adhere to the protocol or applicable regulatory guidelines in conducting the study.

7.0. STUDY PROCEDURES

The scheduled study procedures and evaluations are summarized in Appendix A.

7.1. Demographics, Baseline Medical-Surgical History, Clinical Outcomes

At the time of enrollment, baseline demographics and medical-surgical history (cardiovascular, respiratory, musculoskeletal, gastrointestinal, lymphatic, urinary, nervous, endocrine, skin, reproductive, EENT) will be obtained from the medical charts or from subject interviews. Transplant-specific history (HLA match, organ source, surgical date and select donor and recipient risk factors) will be recorded.

At subsequent visits, changes in the medical and surgical history will be documented (including selected concomitant medications, immunosuppressive drug levels and pathology results from renal biopsies conducted for clinical care). Clinical outcomes will be recorded including subject death, loss of graft function, acute graft rejection or initiation of dialysis.

7.2. Laboratory – Specimen Collection

7.2.1. At Each Screening Visit:

Blood:

- Blood (10 ml) for viral PCR submitted as plasma to UAB Central Laboratory).
- Serum creatinine and GFR performed at local laboratory (or results of assay performed for clinical standard-of-care will be recorded)

Urine:

- specimen (approximately 100 ml) for biomarkers and viral PCR (UAB Central laboratory)
- optional urinalysis (dipstick and microscopic, to include: pH, bilirubin, blood, nitrite, protein, specific gravity, glucose, ketones, RBC/HPF, WBC/HPF, urobilinogen, leukocyte esterase) performed at local laboratory (or results of assay performed for clinical standard-of-care can be recorded)

7.2.2. At Each Intensive Follow-up Visit for Viremic Subjects:

Blood:

- Blood (10 ml) for viral PCR submitted as plasma to UAB Central Laboratory.
- Serum creatinine and estimated GFR – performed at local laboratory (or results of assay performed for clinical standard-of-care will be recorded)

Urine:

- Optional urinalysis (dipstick and microscopic, to include: pH, bilirubin, blood, nitrite, protein, specific gravity, glucose, ketones, RBC/HPF, WBC/HPF, urobilinogen, leukocyte esterase) performed at local laboratory (or results of assay performed for clinical standard-of-care can be recorded)
- specimen (approximately 100 ml) for biomarkers and viral PCR (UAB Central laboratory)

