6.0. SCHEDULE OF EVENTS

6.1. Enrollment Visit (Day 1)

Subjects who meet criteria for the eligibility criteria and have provided informed consent should be scheduled for an Enrollment Visit. The enrollment visit should be scheduled no sooner than 4 weeks after the transplant, but not more than 100 days after the transplant. At the initial Enrollment Visit, the following assessments should be performed:

1. Confirm that informed consent has been obtained and that the subject still wishes to participate;
2. Review the inclusion-exclusion criteria to assure that the patient remains eligible for study participation. Subjects who are not willing or eligible to participate in the clinical trial should be logged as screen failures and reported on the Failed Screening page located on the Central Unit website.
3. Record donor and recipient demographic and risk factor data, to include:
 - a. Donor-derived factors:
 - i. Deceased donor – Standard criteria donor (SCD), Donor after cardiac death (DCD), Expanded criteria donor (ECD)
 - ii. Living donor – related donor or unrelated donor
 - iii. ABO incompatibility
 - iv. Total HLA mismatches
 - v. HLA C7 status
 - vi. Age
 - vii. Race/ethnicity
 - viii. Sex
 - b. Recipient-derived factors:
 - i. Delayed graft function (DGF), defined as use of dialysis within 7 days of the transplant
 - ii. Cold ischemia time (CIT)
 - iii. Warm ischemia time (WIT)
 - iv. Use of stents
 - v. HLA C7 status
 - vi. Type/intensity of immunosuppression, including corticosteroids
 - vii. Acute rejection
 - viii. Age
 - ix. Race/ethnicity
 - x. Sex
4. Document medical and surgical history
5. Document use of selected concomitant medications (specifically, antiviral agents, immunomodulators, and immunosuppressive medications – see the listing provided in

- the MOP). Record all immunosuppressive drugs administered since transplantation, including peri-operative induction therapy with biological agents;
6. Document blood concentrations of immunosuppressive drugs measured for clinical reasons;
 7. Obtain blood for serum creatinine determination and estimated GFR (if these studies were performed for routine standard-of-care within 7 days prior to enrollment, then the results of those assays can be recorded for study purposes);

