APPENDIX A-1: Table of Study Procedures - Screening Phase

Procedures	^A 4 weeks to 100 days Baseline	Month 1	Month 2	Month 3	Month 4	Month 5	Month 6	Month 8	Month 10	Month 12
¹ Review informed consent	X									
Assess eligibility criteria-inclusion/exclusion	X									
^{1a} Record medical/ surgical history	X									
² Record donor and recipient risk factor data	X									
^{2a} Record Specific Interval History Data		X	X	X	X	X	X	X	X	X
³ Record IS drug trough levels	X	X	X	X	X	X	X	X	X	X
⁴ Obtain ≥ 10 mL of blood for viral load by PCR	X	X	X	X	X	X	X	X	X	X
⁴ Obtain approximately 100 mL of urine for PCR and for biomarkers	X	X	X	X	X	X	X	X	X	X
⁵ Record selected concomitant medications	X	X	X	X	X	X	X	X	X	X
⁶ Serum Creatinine, estimated GFR (local lab)	X	X	X	X	X	X	X	X	X	X
⁷ Urinalysis - optional (local lab)	X	X	X	X	X	X	X	X	X	X
⁸ Study Termination										X

LEGEND

^A The post-transplant specimen collection and study procedures should not be implemented until 4 weeks (out to 100 days) post-transplant

¹ The informed consent may be obtained during the peri-transplant admission (as early as T-7 days) out to T+100 days^{1a} The medical history includes assessment of the following: cardiovascular, respiratory, musculoskeletal, gastrointestinal, lymphatic, urinary, nervous, endocrine, skin, reproductive and EENT Surgical history includes organ source, and date of surgery .

² Record donor/recipient risk factors data: donor= [deceased, living, ABO incompatibility, total HLA mismatches, HLA C7, age, race/ethnicity, sex] recipient= [delayed graft function(DGF), cold ischemia time (CIT), warm ischemia time (WIT), use of stents, HLA C7 status, type/intensity of immunosuppression, acute rejection, race/ethnicity, age, sex]

^{2a} Subject death, loss of graft function as defined by GFR <10 mL/min/1.73 m², development of urinary outlet obstruction, development of gross hematuria, development of lymphocele acute rejection, initiation of dialysis, re-transplantation, renal biopsies – Should renal biopsy be performed per standard-of

³ Record lab results for immunosuppressive drug trough levels, if performed for standard of care

⁴ Collect and process blood and urine samples according to instruction outlined in Manual of Procedure

⁵ Record selected concomitant medication generic name dosage, start/stop date, and route of administration, failure to record, report as a protocol deviation.

⁶ Record results of serum creatinine and estimated, if obtained for standard of care.

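### GFR for a primary objective is taken as each local or clinical laboratory reports it; computing it centrally with one equation would cost almost nothing

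*Combined protocol and SAP*

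**What the plan says.** **Source of the values.** For screening visits, Section 7.2.1 specifies "Serum creatinine and GFR performed at local laboratory", or else the recorded result of a standard-of-care assay. For intensive visits, Section 7.2.2 has "Serum creatinine and estimated GFR – performed at local laboratory", with the same standard-of-care alternative. One subsection says GFR and the other estimated GFR. Appendix A-1 lists "Serum Creatinine, estimated GFR (local lab" at every visit, and A-2 lists it at each two-weekly and follow-up visit.

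**Substitution.** Sections 6.1 and 6.2 accept routine results from the 7 days before the visit. Section 6.3 reads: "If results of serum creatinine and GFR obtained for clinical care purposes (within 7 days) are available, those results may be used instead".

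**What is already recorded.** Section 6.1 says "Obtain blood for serum creatinine determination and estimated GFR", so creatinine is held beside the GFR value. Baseline recipient factors in Appendix A-1 include "type/intensity of immunosuppression, acute rejection, race/ethnicity, age, sex".

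**Use of GFR.** The association between viremia and GFR decline is the second primary objective (3.1.1) and is part of the study hypothesis (8.1). Section 8.2.1 powers it, beginning "We are also interested in comparing the change in GFR between those with and without BKV viremia". Section 8.4.1 analyses it with a mixed model for repeated measures that names no site, laboratory or equation term. Section 3.2.2 also uses an absolute GFR below 10 ml/min/1.73 m² to define loss of graft function. Section 3.2.1 does not list GFR among the primary endpoints.

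The protocol nowhere names an estimating equation, requires a common one, or gives the coordinating center the task of calculating GFR.

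**The concern.** The same creatinine can give different GFR values under different equations. With about six sites, local laboratories and clinical results allowed as substitutes, the plan leaves the equation to whoever reports the value. The consequences differ by type of discrepancy:

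- A constant offset that stays with a subject drops out of change from baseline.
- A proportional difference rescales the change.
- A switch of equation between two visits of one subject goes straight into that subject's change. The substitution rule does not exclude this.
- An absolute threshold such as GFR below 10 has no cancellation, so the same patient could meet it at one site and not at another.

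BK viral load, by contrast, is assayed in a central laboratory, with a planned comparison against site results (Sections 7.5 and 8.4.3). GFR has no equivalent, yet the ingredients for a uniform calculation are already collected.

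**Working it through.** **Inputs from Section 8.2.1.** SD of change 10.9 ml/min/1.73 m² in both groups; 40 viremic and 410 non-viremic subjects; difference 5.9; 90% power; 5% level; t-test. Sidedness is not stated and is taken as two-sided.

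**Step 1: the plan's own figure.** SE = 10.9 × √(1/40 + 1/410) = 1.806. The noncentrality is 5.9/1.806 = 3.27 on 448 degrees of freedom, which gives power of 90.3%. The difference detectable with exactly 90% power is 5.87. The stated 5.9 is reproduced. A one-sided test would give about 94.8% (normal approximation), so two-sided is the matching reading.

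**Step 2: one equation per subject throughout.**

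- Constant offset c: (G12 + c) − (G0 + c) = G12 − G0, so there is no effect.
- Proportional factor varying between sites with mean 1 and CV 10% (assumed): SD = 10.9 × √(1 + 0.10²) = 10.95, and power is about 90.0%.

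**Step 3: switching within subjects.** Assume a share q of subjects has the enrollment and Month 12 values from equations that differ by b, with either direction equally likely. The SD of change becomes √(10.9² + q × b²). For q = 10% and b = 5 this is √(118.81 + 2.5) = 11.01. The documents give neither q nor b, so a range is shown as SD / power at 5.9:

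| Share switching | b = 3 | b = 5 | b = 8 |
|---|---|---|---|
| 10% | 10.94 / 90.1% | 11.01 / 89.7% | 11.19 / 88.8% |
| 25% | 11.00 / 89.8% | 11.18 / 88.8% | 11.61 / 86.5% |
| 50% | 11.10 / 89.3% | 11.46 / 87.3% | 12.28 / 82.5% |

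If all switches go the same way, the added SD is b × √(q(1 − q)). For b = 5 that is at most 5 × √(0.5 × 0.5) = 2.5. The common shift cancels between groups when q is the same in both.

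**Step 4: bias.** Bias in the group contrast is the difference in one-directional switching share times b. A 20-percentage-point imbalance with b = 5 (both assumed) gives 0.20 × 5 = 1.0, which is 1.0/5.9 = 17% of the planned difference. With equal switching it is zero.

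**Step 5: if 10.9 already contains equation noise.** The SD comes from a cited publication, and the documents do not say how GFR was derived there. If 10.9 includes noise with SD 2, removing it gives √(10.9² − 2²) = 10.71 and power of 91.3%. With SD 3 it gives 10.48 and 92.4%. On this reading, a common equation is a small gain over the plan's figure.

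All of this uses the plan's two-point t-test. The planned mixed model uses every visit, so these figures indicate size and do not predict its power.

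**The case against.** The documents are silent on equations, and silence does not show that sites differ. A reader might infer that mixed equations do occur, but nothing in the protocol says so. The Data Management Plan and Manual of Procedures were not available and could hold a derivation. The protocol cites the Manual for matters such as specimen handling and medication lists, not for GFR.

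Frequent switching is also not documented. Section 4 expects most samples to be collected at routine clinic visits, so a substituted clinical result may well come from the same local laboratory. The protocol mentions a reference laboratory for BK PCR, not for creatinine.

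A reader might also set a switch of a few ml/min against the 5.9 target and conclude that the comparison is seriously threatened. That compares an error in one subject's value with a difference in group means; non-differential errors largely average out. Likewise, an added SD of 4 might be assumed. With a 5-unit switch, that would need 64% of all subjects to switch in random directions (5 × √0.64 = 4), which nothing in the documents supports.

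These objections stand, and they limit the size. They do not remove the gap: a value that serves a primary objective has no stated derivation, absolute cut-offs get no protection from cancellation, and a uniform calculation is available from data already collected.

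**Conclusion.** The point holds as an inexpensive improvement to an analysis variable. The plan permits different equations across sites and within a subject. It does not show that either happens. If each subject stays on one equation, the effect on the change comparison is negligible. The moderate assumption of 10% to 25% of subjects switching by 5 ml/min/1.73 m² costs roughly 0.6 to 1.5 percentage points of power. A loss of several points needs widespread switching or larger differences between equations.

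Bias requires switching to be related to viremia status. Viremic subjects follow a different visit schedule, so this cannot be ruled out, but the documents give no evidence for it. The clearest non-cancelling use is the absolute graft-loss cut-off.

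Calling the GFR comparison primary rests on Sections 3.1.1 and 8.4.1; Section 3.2.1 does not list it, and the three should be reconciled.

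**What to change.** - **Section 8.4.1:** state that, for all visits and sites, the data coordinating center computes the analysis eGFR from recorded serum creatinine, age and sex (and race only if the chosen equation requires it), using one equation named before analysis.
- **Sensitivity analysis:** keep the laboratory-reported eGFR and repeat the GFR model with it.
- **Section 3.2.2:** say which GFR value the graft-loss cut-off refers to.
- **Section 7.2:** use the same term, GFR or estimated GFR, in both subsections.
- **Optional:** add a site term to the mixed model. One equation does not remove differences between creatinine assays, and a site term can absorb some of what remains. It does not correct switching within a subject, so it does not replace the common equation.

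The cost is a sentence or two and one derived variable. No extra sample, visit or data field is required.
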